3.2 Primary endpoints

- Predict neurocognitive decline based on RT dosimetric and other explanatory variables like gender, age at diagnosis, comorbidities, level of education, social factors such as social activity and occupation, tumour size and localization, pathological/genetic/molecular characteristics, therapy protocols (surgery, radiotherapy and/or chemotherapy) in an NTCP model for each cognitive domain
- Measure the prevalence and severity of neurocognitive decline compared to baseline at one year, for all cognitive domains (attention, memory, working memory, information/visuomotor processing speed, executive functioning)

3.3 Secondary endpoints

- Identify early and late changes on structural and functional MR imaging
- Evaluate associations between neurocognitive functioning and RT dosimetry

3.4 Trial Design

This is an observational cohort study which evaluates primary brain tumour patients longitudinally at the following timepoints: baseline (minimal 4 weeks after surgery (if indicated), before radiotherapy), three months (+/- 2 weeks) after end of radiotherapy, 1 year after end of radiotherapy (+/- 1 month) and 2 years after end of radiotherapy (+/- 1 month). At each visit, neurocognitive testing, a self-report inventory and/or advanced MR imaging will take place. During and after radiotherapy and at each follow-up visit, adverse events will be monitored using CTCAEv5.0²⁰.

3.5 Study Flowchart

4. Selection and withdrawal of subjects

4.1 Inclusion criteria

 Adult patients (≥ 18 years at the time of diagnosis) with a primary brain or base of skull tumour, who are amenable for conventionally fractionated radiotherapy (photon or proton irradiation)

4.2 Exclusion criteria

- Patients with tumours with poor prognostic characteristics
 - Grade IV glioblastoma
 - IDH1/2 wild type glioma
 - o grade III meningioma
 - H3K27M midline glioma
- Patients with tumours requiring craniospinal irradiation (CSI)/whole ventricular irradiation (WVI):
 - o Medulloblastoma
 - o **Germinoma**
 - Ependymoma requiring CSI
- Hypofractionated/stereotactic radiation (fraction sizes > 2 Gy per fraction)
 - o AVM
 - Acoustic schwannoma
 - o Brain metastasis
- Inability to perform the cognitive tests or self-report inventories because of motor/sensory deficits or insufficient Dutch language proficiency
- Mental retardation documented before diagnosis
- Pre-diagnosis/pre-existing psychiatric diagnosis resulting in cognitive deficits like psychoses, neurodevelopmental disorders (autism/learning disorders)
- Relapse priory treated by chemo and/or radiation therapy
- Genetic syndrome (e.g. Down)
- Unable to perform MR imaging (claustrophobia, metallic implants like pacemaker/ICD/neurostimulator)

4.3 Expected duration of trial

Each participant will be followed at least for two years after radiotherapy. The trial will be regarded as completed when 120 patients will have reached a follow-up of two years. Since neurocognitive decline is considered to be progressive, participants will still be in follow-up after completion of the trial according to the clinical practice guidelines.

4.4 Subject discontinuation or withdrawal

Participation can be discontinued at any time if the subject, the Investigator, or the Sponsor feels that it is not in the subject's best interest to continue. The following is a list of possible reasons for study treatment discontinuation:

- Screening failure
- Subject withdrawal of consent
- Subject is not compliant with study procedures
- Lost to follow-up
- Sponsor request for early termination of study
- Subject death
- Progressive disease or relapse during follow-up

All subjects are free to withdraw from participation at any time, for any reason, specified or unspecified, and without prejudice. Reasonable attempts will be made by the Investigator to provide a reason for subject withdrawals. The reason for the subject's withdrawal from the study will be specified in the subject's source documents and the Case Report Form (CRF). The Investigator will make every effort to contact subjects who are lost to follow-up. Attempts to contact such subjects must be documented in the subject's records (e.g., times and dates of attempted telephone contact, receipt for sending a registered letter, etc.). Subjects who prematurely discontinue are not to be replaced. For subjects considered lost to follow-up, the CRF must be completed up to the last visit performed.

5. Trial Procedures

Subjects will be screened at the consultation of the neurosurgeon (after biopsy or surgery) or after physician referral to the local radiotherapy-oncology centre. This study will be listed at www.clinicaltrials.gov.

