7.2 Analysis

Analyses and statistical methods will be applied to all subjects.

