7.2.1 Neuropsychological data

The following research questions are addressed by using multiple statistical tests.

- 1. How severe is the neurocognitive decline after treatment and how does it change over time?
- 2. Which neurocognitive domains are affected in which patients?

The first question is addressed by investigating the neurocognitive performance of primary brain and base of skull tumour patients. The performance on neurocognitive measures of the patients will be assessed at 3 timepoints over time. The raw test-scores are converted to normalized zscores based on normative data for each cognitive test. For each cognitive test, cognitive impairment is defined as a z-score \leq 1.5, and patients will be dichotomized according to their impairment status (impaired versus unimpaired). The frequency of impairment will be reported as descriptive information.

We will assess the evolution in the z-scores with a mixed repeated measures model to test changes throughout time. However, if the data are not normally distributed, the Friedman test will be used as alternative approach. The effects of the patient- and treatment-related predictors on the neuropsychological and questionnaire scores will be investigated using general linear models (predictors= tumour location, radiation dose, covariates= gender, age at treatment, time since treatment and socio-economic status) at each timepoint. Bonferroni correction will be applied as

method for statistical correction of multiple tests, for each test outcome (n=5 outcomes; memory, executive functioning, attention, visuomotor function, working memory) that is predicted.

Effect sizes of the tests will be reported. Partial eta squared (hp2) will be computed to estimate effect sizes (weak effect: $np^2 \approx 0.03$; moderate: $np^2 \approx 0.06$; large: $np^2 \geq 0.14$) for linear relationships between predictor and each outcome (e.g. age, time since treatment). Cohen's d will be used to estimate effect sizes for subgroup differences (small effect: 0.2 < d < 0.3; medium: 0.3 < d < 0.8; large: d > 0.8).

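### Section 4.4 lets a patient be taken off study for not complying with study procedures, which permits avoidable loss of follow-up related to the cognitive outcome

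*Protocol*

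**What the plan says.** Section 4.4 gives a general rule: "Participation can be discontinued at any time if the subject, the Investigator, or the Sponsor feels that it is not in the subject's best interest". A list follows, introduced by "The following is a list of possible reasons for study treatment discontinuation". One entry is "Subject is not compliant with study procedures"; the others include withdrawn consent, loss to follow-up, death and progression. Non-compliance is not defined, and a missed procedure is not distinguished from leaving the study. On numbers, the section states: "Subjects who prematurely discontinue are not to be replaced". On data, it states: "For subjects considered lost to follow-up, the CRF must be completed up to the last visit performed".

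The second primary endpoint in 3.2 is: "Measure the prevalence and severity of neurocognitive decline compared to baseline at one year, for all cognitive domains". The visit table in 5.1 places cognitive testing at baseline, 1 year and 2 years, and MRI at baseline, 3 months and 1 year. Section 7.2 says: "Analyses and statistical methods will be applied to all subjects".

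**The concern.** The study gives no study treatment, so the only thing section 4.4 can stop is follow-up. The procedures a patient might fail to comply with are about one hour of cognitive tests (5.2), about 30 minutes of questionnaires (5.3) and up to 60 minutes of MRI (5.4). Attending and completing them draws on memory, attention and executive function, which are among the abilities whose decline is the outcome. Non-compliance is therefore plausibly related to the outcome, and a rule that allows follow-up to end because of it can select against decliners. At stake are the 1-year prevalence and severity estimates and the number of events available to the NTCP models.

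**Working it through.** **1. How a test that could have been done is lost.** In the 5.1 table, MRI is the only study assessment marked at 3 months (6.2 also asks for a toxicity form at every follow-up visit). The next cognitive test is at 1 year. A patient who misses or declines the 3-month MRI meets the wording of the non-compliance entry. If discontinued then, the patient has a baseline score and no 1-year score.

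**2. What the analyses can do without that score.** The longitudinal analysis is described as: "We will assess the evolution in the z-scores with a mixed repeated measures model to test changes throughout time". That model can still use the baseline value. Three other parts cannot make up for the loss:
- the 1-year comparison with baseline needs a 1-year result;
- the logistic NTCP models (7.2.4) need an outcome status for each patient;
- the Friedman test, the fallback in 7.2.1, needs complete cases.

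**3. The plan's own sample-size figures (7.1).** A two-sided paired t-test at 0.05 reproduces them:
- d = 0.368: n = 60 gives power 0.801 and n = 120 gives 0.979 (stated 0.800 and 0.979).
- d = 1.271: n = 8 gives power 0.867 (stated 0.868).

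At d = 0.368, losing 10%, 20%, 30% or 40% of 120 leaves 108, 96, 84 or 72 patients, with power 0.966, 0.946, 0.915 or 0.869. Power for the change test is not the problem. For the prediction models, 7.1 asks for 90 patients at event rate 0.2 and 120 at event rate 0.5 (taken as stated, not reproduced). Against 120 planned, the slack is (120 - 90)/120 = 25% at the low rate and none at the high rate.

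**4. Size of the bias.** Let q be the fraction of patients discontinued under this entry who would otherwise have been tested at 1 year. Let p_off be their event rate and p_on the event rate in the rest. With no other loss:

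true prevalence = (1 - q) x p_on + q x p_off; reported = p_on; shortfall = q x (p_off - p_on).

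The protocol gives neither q nor p_off. Only the overall event-rate range of 0.2 to 0.5 comes from 7.1; the rest is assumed.
- q = 0.10, p_on = 0.3, p_off = 0.7: true = 0.9 x 0.3 + 0.1 x 0.7 = 0.34; reported 0.30; shortfall 0.10 x 0.4 = 4 points. Of 120 x 0.34 = 40.8 events, 12 x 0.7 = 8.4 are lost.
- q from 0.05 to 0.15, p_on from 0.2 to 0.5, p_off from 0.5 to 0.8: the shortfall runs from 0 (0.5 against 0.5) to 0.15 x (0.8 - 0.2) = 9 points.

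The range is wide because the inputs are unknown. It includes zero, and any positive value follows from assuming that the lost patients have the higher event rate.

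**The case against.** The strongest reply is that 4.4 orders nothing. Discontinuation is discretionary and tied to the patient's best interest, and the list gives only possible reasons. No missed test, questionnaire or MRI triggers it. Section 4.3 expects at least two years of follow-up for each participant, and 5.1 ties the end-of-study visit to two years or progression, not to non-compliance. All of this stands. A reader might infer that patients who miss procedures are removed from the cohort or from the analysis; the documents do not support that, because 7.2 applies the analyses to all subjects and no passage discards collected data. But 7.2 cannot supply a score that was never obtained, and undefined discretion used at three centres leaves the selection risk open.

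A second reply is that a patient who cannot or will not be tested at 1 year has no score with or without this entry. That also stands and limits the point to patients who could still have been tested.

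A third concerns MRI. A reader might infer that the primary endpoints need only the test battery and the radiotherapy plan, so that a refused MRI is harmless. That goes too far. Section 3.2 puts education, comorbidities and social factors into the models, 5.3 collects some of this by questionnaire, and the second NTCP effort in 7.2.4 uses heat maps whose source is not defined. What holds is narrower: 1-year prevalence and the first NTCP effort, built on atlas dose metrics and clinical factors, do not depend on follow-up MRI.

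Finally, missing-data handling may be in a SAP that is not shown. A SAP can model missing visits, but it cannot recover visits that the protocol allowed to be stopped.

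**Conclusion.** The point holds as a modest, cheaply avoidable weakness in 4.4. The entry permits discontinuation for a reason that may be caused by the outcome, and the study treatment wording does not suit an observational design. The likely effect is to understate decline, on two assumptions: that non-compliance is more frequent among decliners, which is plausible but not stated in the protocol, and that investigators use the entry.

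No firm size can be given. The 4-point figure is an illustration under assumed inputs. It becomes an upper figure if the 10% counts everyone taken off for non-compliance, because some of them would have been untestable anyway. A reader might also infer that this entry alone brings the evaluable number below the 120 in 7.1. Any attrition without replacement does that, and by the plan's own figures 90 suffice at event rate 0.2. The entry adds to the loss; it is not its sole cause.

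**What to change.** Amend section 4.4 as follows:
- Delete non-compliance with study procedures from the list, and reword the lead-in to refer to discontinuation of study participation. Leave the other listed reasons unchanged.
- State that a patient who misses or declines a procedure, including MRI, stays in follow-up and is invited to all remaining cognitive test visits unless consent is withdrawn.
- Require the reason for each missed cognitive test to be recorded. At present 4.4 asks for reasons only for withdrawals from the study.

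The cost is a short amendment and some continued contact with patients who attend irregularly. The right to withdraw is unaffected. The change will not recover tests from patients who cannot be assessed; it only keeps the protocol from ending follow-up of those who still can be.

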5.1 By visit

Each patient will have 5 trial visits. The sequence of procedures to be performed at each visit is detailed below.

		SCREENI							END
		NGS PHASE	FOLLO	V-UP	PHASE				OF STUDY
Visit name	Protocol	Screenings visit	Baseline visit*	RT start	End of RT	3 months after	1 year after RT	2 years after RT	End of study visit°
Day				DO	Dstop	3 M	12 M	24M	24 M
Visit window	3.4	D-28 to 0	D -21 to 0		+/- 3D	+/- 2 W	+/- 4 W	+/- 4W	+/- 8W
Informed consent	IC	x							
Eligibility criteria assessment	4	x							
Patient information and history ^a	R	x							
Tumour characteristics ^a	R	x							
RT charachteristics ^a	R				x				
Questionnaires ^b	5.3		x				х	х	
Neurocognitive testing ^c	5.2		x				x	x	
MRI ^d	5.4		x			х	х		
RT plan ^d					x				
CRF toxicity ^a	6.2			x	х				х

End of study	R					х
assessment						

*: minimally 4 weeks after surgery

IC: informed consent form

R: REDCap

o: after 2 years or at progression

a: in REDCap (by CTA or MD)

b: in REDCap (online survey, filled in by patient via REDCap platform)

c: in REDCap (by neuropsychologist)

d: to upload coded DICOM images and RT plan in OncoPlace (by CTA)

5.2 Neurocognitive assessment

We will perform a standardized neurocognitive test battery in all patients at baseline (prior to RT) and each consecutive year (1 year and 2 years post-RT). The acquisition of neurocognitive assessments takes approximately 1 hour. Results will be followed over time and compared to normative data ^{21,22}.

All these tests and questionnaires have been extensively described and used to quantify neurocognitive functioning in adults. Both neurocognitive testing and completion of the questionnaires takes place in the hospital.

We will use a broad evaluation of neurocognitive performance.

- The Montreal Cognitive Assessment (MOCA), is a screening instrument for cognitive deficits in multiple domains²³.
- Trail Making Task (TMT)²⁴, is an executive task which requires to link characters and digits in the correct sequence.
- Digit span (subtest of the Wechsler Adult Intelligence Scale(WAIS))²⁵ is a working memory task, which requires to repeat digits in same, reversed and sequencing order.
- The Hopkins Verbal Learning Test- Revised (HVLT-R)²⁶ is a verbal memory task for which participants need to repeat 12 words (three repetitions of free-recall) to assess verbal learning. Afterwards, they are asked to repeat or recognize the memorized words (Delayed recall and recognition).
- Controlled Word Association Test (COWAT)²⁷ assesses categoric and phonemic fluency. The participant is required to make verbal associations to a category or different letters of the alphabet by saying all the words which they can think of in this category or beginning with a given letter.
- The Stroop Color and Word Test (SCWT)²⁸ assesses the ability to inhibit cognitive interference that occurs when the processing of a specific stimulus feature impedes the simultaneous processing of a second stimulus attribute.
- The digit symbol substitution test of the WAIS (coding)²⁹ measures processing speed. This test consists of digit-symbol pairs followed by a list of digits. Under each digit the subject

should write down the corresponding symbol as fast as possible. The number of correct symbols within the allowed time is measured.

Cognitive domain	Neurocognitive test	Outcome measurement time				
Attention	TMT B					
Memory	HVLT immediate recall	Sum score - learning				
	HVLT delayed recall	Sum score				
	HVLT recognition	Good recognition-mistakes				
	WAIS IV digit span forward	Total number of series				
Executive functioning	COWAT	Sum of words				
	SCWT	Interference score				
Working memory	WAIS IV digit span backwards	Total number of series				
Information/visuomotor	WAIS IV digit span sequencing	Total number of series				
processing speed	WAIS IV symbol substitution	Sum score				
	TMT A	Time				

Cognitive tests grouped per cognitive domain and defined outcome measurement. TMT= trail making test, HVLT= Hopkins Verbal Learning Test, COWAT= Controlled Oral Word Association Test, SCWT= Stroop Color Word Test, WAIS= Wechsler Adult Intelligence Scale

5.3 Questionnaires

Daily life functioning will be examined with neuropsychological questionnaires. This self-report inventory will take about 30 minutes. All participants will complete:

- The EORTC brain cancer module (EORTC QLQ-BN20)³⁰ to assess health-related quality of life and symptoms in these brain cancer patients.
- The Spielberger State-Trait Anxiety Inventory³¹ to assess anxiety levels.
- The Beck Depression Inventory-II^{32,33} to estimate depressive symptoms.
- The Cognitive Failure Questionnaire (CFQ)³⁴ to address cognitive problems in daily life.
- The Behavior Rating Inventory of Executive Function (BRIEF-A)³⁵ to assess specific problems in executive functioning.
- The EORTC QLQ-C30 questionnaire³⁶ to assess general quality of life.
- The Functional Assessment of Chronic Illness Therapy Fatigue (FACIT-F) Scale³⁷ to investigate an individual's level of fatigue during their usual daily activities over the past week.

• The Pittsburgh Sleep Quality Index (PSQI)³⁸ assesses sleep quality over a one month time interval.

Socio-economic status (educational level of parents and participants) and medical conditions are evaluated at baseline, 1 year and 2 years post-RT with a separate questionnaire. This questionnaire will take maximum 5 minutes.

5.4 MRI imaging

We will perform an advanced MR protocol in every patient. No gadolinium contrast will be administered. Advanced MRI will be performed in all patients prior to RT (baseline), at three months, and at one year post-RT. All subjects will be imaged on the same scanner in each center (UZ Leuven: 3T Philips with a 32-channel phased-array head coil, located in the radiology department at UZ Leuven). Phantom scans will be used to adapt each protocol in every center. Neuroimaging will consist of:

- 3D high-resolution T1-weighted magnetization-prepared rapid acquisition gradientecho (MPRAGE) anatomical scan for grey/white matter volumetry
- o 3D T2-weighted FLAIR to examine leukoencephalopathy
- Advanced diffusion weighted- imaging (DWI). DWI is a technique enabling the visualization and characterization of the WM architecture via the self-diffusion of water molecules allowing us to study potential therapy-induced changes in the WM microstructure. Damage to WM structures for example axonal loss or demyelination may change quantitative DWI parameters such as fractional anisotropy (FA), mean diffusivity (MD) and diffusion kurtosis.
- Resting state functional MRI (rfMRI) to estimate neuronal activity of the brain at rest (examination with eyes closed). rfMRI uses the vascular response nearby electrically active neurons to indirectly visualize brain activity and allows us to determine the functional coherence (or so-called "connectivity") between the different brain regions at rest. Participants will therefore be asked to close their eyes during the examination, but not to fall asleep.
- Susceptibility-weighted MR imaging (SWI) to detect radiation therapy-induced cerebral microbleeds.
- Arterial Spin labeling (ASL) to measure tissue perfusion.

The duration of the proposed scan protocol is maximum 60 minutes.

6. Assessment of Safety

6.1 Specification of safety parameters

As the oncological treatments (radiotherapy, chemotherapy and/or surgery) and MR imaging are currently being used as standard of care, the study team does not anticipate subjects experiencing any adverse events solely due to being in the study. This is simply a proposal to evaluate and follow subjects undergoing these commonly performed procedures, both of which have been shown to be safe and approved.

Specifically for the MR imaging, the standard safety measures will be respected. Patients will be instructed to remove all metallic objects from pockets and hair, as well as metallic jewellery. Additionally, any individual that goes into the MRI scanner room will be required to follow these same instructions and procedures. Patients will be asked to fill out a screening form asking about anything that might create a health risk or interfere with the MRI exam. Items that may create a health hazard or other problem during an MRI include:

- Certain cardiac pacemakers or implantable cardioverter defibrillators (ICDs)
- Ferromagnetic metallic vascular clips placed to prevent bleeding from intracranial aneurysms or blood vessels
- Some external or implanted medication pumps (such as those used to deliver insulin, pain-relieving drugs, or chemotherapy)
- Certain cochlear (i.e., for hearing) implants
- Certain neurostimulation systems
- Catheters that have metallic components
- A bullet, shrapnel or other type of metallic fragment
- A metallic foreign body located within or near the eye (such an object generally can be seen on an x-ray; metal workers are most likely to have this problem)

In addition, subjects may be harmed by:

• Loud noise from the MRI device. All subjects will be given ear protection to prevent risks from loud noise.

• Some subjects may experience mild transient vertigo and/or metallic taste when they are being moved into the MRI system.

